2.8 Analysis of the key secondary objective

Secondary variables consist of both efficacy and safety variables.

2.8.1 Efficacy variables

MS relapses that occur while on study will be summarized by cohort for the FAS. The number of patients with at least one relapse, along with the total number of episodes across all patients, will be presented. The proportion of episodes requiring steroid use, proportion requiring hospitalization, and proportion at each severity level will be summarized. All steroid treatment of MS relapses will be coded by World Health Organization (WHO) drug anatomical therapeutic chemical (ATC) classification. All steroid treatment of MS relapses will be summarized by ATC level 2 and preferred term.

All past and present MS symptoms will be listed for the FAS.

The following additional efficacy variables will be analyzed by cohort using data from patients in FAS.

1. Change from Baseline in Patient Determined Disease Steps (PDDS);
2. Change from Baseline in T2 lesion burden;
3. New Gd-enhancing T1 lesion count

Descriptive statistics (sample size, mean, standard deviation, standard error of mean, minimum, first quartile, median, third quartile, interquartile range, and maximum) will be provided. The 95% confidence interval for the mean will be calculated.

2.8.2 Safety variables

The Safety Set will be used for the following analyses.

1. The assessment of safety will be based mainly on the frequency of adverse events.
2. Change from Baseline to Months 3, and 12 in CD4+ naïve T cells (CCR7+CD45RA+);
3. Change from Baseline to Months 3, and 12 in CD4+ central memory T cells (CCR7+CD45RA-CD45RO+);
4. Change from Baseline to Months 3, and 12 in CD4+ effector memory T cells (CCR7-CD45RA-CD45RO+);
5. Change from Baseline to Months 3, and 12 in CD4+ Th1 cells (CXCR3+);
6. Change from Baseline to Months 3, and 12 in CD4+ Th2 cells (CCR4+);
7. Change from Baseline to Months 3, and 12 in CD4+ Th17 cells (CCR6+);
8. Change from Baseline to Months 3, and 12 in CD8+ naïve T cells (CCR7+CD45RA+);
9. Change from Baseline to Months 3, and 12 in CD8+ central memory T cells (CCR7+CD45RA-CD45RO+);

10. Change from Baseline to Months 3, and 12 in CD8+ effector memory T cells (CCR7- CD45RA-CD45RO+);
11. Change from Baseline to Months 3, and 12 in naïve B cells (CD19+CD27-);
12. Change from Baseline to Months 3, and 12 in memory B cells (CD19+CD27+);
13. Change from Baseline to Months 3, and 12 in regulatory B cells (CD19+CD24+CD38+);
14. Change from Baseline to Months 3, and 12 in monocytes (CD14+);
15. Change from Baseline to Months 3, and 12 in neutrophils (CD16+);
16. Change from Baseline to Months 3, and 12 in NK cells (CD56+);
17. Change from Baseline to Months 3, 6, and 12 in the anti-JCV antibody index;
18. Change from Baseline to Months 3, 6, and 12 in Hematology measurements;
19. Anti-JCV antibody status (+ or -) at Months 3, 6, and 12.
20. Change from Baseline to Months 3, and 12 in Total CD4+ Absolute Cell Counts
21. Change from Baseline to Months 3, and 12 in Total CD4+ Differential Cell Counts
22. Change from Baseline to Months 3, and 12 in Total CD8+ Absolute Cell Counts
23. Change from Baseline to Months 3, and 12 in Total CD8+ Differential Cell Counts
24. Change from Baseline to Months 3, and 12 in Total CD19+ Absolute Cell Counts
25. Change from Baseline to Months 3, and 12 in Total CD19+ Differential Cell Counts

For safety Variable 1, please refer to section 2.11.4 for more details.

For safety Variable 19, the frequency count and percentage together with the 95% confidence interval for the proportion of JCV antibody positive patients will be presented. The shift from baseline to Months 3, 6, and 12 in anti-JCV screening index will also be summarized.

For safety Variables 2–18, descriptive statistics (sample size, mean, standard deviation, standard error of mean, minimum, first quartile, median, third quartile, interquartile range, and maximum) will be provided. The 95% confidence interval for the mean will be calculated.

In addition, correlation coefficients between changes in cellular (T, B and monocyte, neutrophil, NK) subsets and efficacy (MRI based variables and PDDS) and safety outcomes (anti-JCV antibody status and index) will be computed. Analyses of safety data will be by cohort based on the Safety Set.

2.8.3 Handling of missing values/censoring/discontinuations

No imputation will be performed for safety endpoints.

2.8.4 Adverse events (AEs)

All AE verbatim descriptions will be coded using the Medical Dictionary for Regulatory Activities (MedDRA), Version 19.1 or the most updated version.

Treatment-emergent adverse events (TEAEs) are defined as AEs that started or worsened in severity on or after the first dose of fingolimod treatment and no later than the last treatment date + 14.

All TEAEs will be summarized by presenting the number and percentage of patients having at least one TEAE, and the number of TEAEs that occurred in each System Organ Class (SOC) and Preferred Term (PT). A patient with multiple occurrences of an AE will be counted only once in the corresponding AE category.

In the TEAE summary outputs, adverse events will be sorted by descending percent of patients.

The AE summaries below will be performed:

- An overall summary of the number and percentage of patients

- TEAEs, regardless of fingolimod relationship by SOC and PT
- TEAEs suspected to be fingolimod-related by SOC and PT
- TEAEs, regardless of fingolimod treatment relationship by SOC, PT and maximum severity

TEAEs starting after the first dose of fingolimod treatment with a missing severity will be classified as severe. If a patient reports a TEAE more than once within that System Organ Class (SOC)/ Preferred Term (PT), the AE with the highest severity will be used in the corresponding severity summaries.

2.8.4.1 Deaths and Serious Adverse Events

TEAEs leading to Death are those events with “Outcome” response recorded as “Fatal” on the Adverse Events page of the eCRF. Number of patients with TEAEs leading to death will be summarized by SOC and PT. A listing of all TEAEs leading to death will be provided.

All reported deaths will be listed. Death will also be summarized for overall and for on treatment period (from first dose to 14 days after last dose). The number of deaths and the primary cause of death will be presented by treatment group in the summary table.

Serious adverse events are those events with a response of “Yes” for the item “Was AE Serious” on the AE form. Summaries of incidence rates (frequencies and percentages) of serious AEs by SOC and PT will be prepared. A patient data listing of all SAEs will be provided.

In summary, following summaries of TEAEs will be provided:

- TEAEs leading to death, by SOC and PT
- Serious TEAEs, regardless of fingolimod treatment relationship, by SOC and PT
- TEAEs leading to fingolimod treatment discontinuation, regardless of fingolimod treatment relationship, by SOC and PT

Listings to be provided are :

- AEs leading to Deaths (CRF Adverse Event page: AE outcome is Fatal.)
- Serious AEs
- AEs leading to dose discontinuation

2.9 Interim analysis

Two interim analyses of data will be performed prior to the final analysis at Month 12.

1. The first interim analysis is an early assessment to evaluate safety in Cohort 2 patients. This will be conducted when 50% of patients in Cohort 2 have completed the Month 6 follow up. For this analysis, primary variables, demographics, baseline characteristics, adverse events, and serious adverse events will be summarized.
2. The second interim analysis is the primary analysis for this study. This analysis will be conducted when all patients in Cohorts 1 and 2 complete Month 6 (primary time point of interest) of study. All data collected on patients from both Cohorts 1 and 2 will be included in this analysis. These data will be analyzed as mentioned in protocol Sections 9.4, 9.5, and 9.6.

This is an open-label, single arm study, and has no active control. The first interim analysis is a summarization of data from Cohort 2 only and no confirmatory hypothesis will be tested. Thus, the multiplicity adjustment of the level of significance for the primary analysis due to the first interim analysis is not relevant in this study. Results obtained from these interim analyses may be reported and published externally for communication to health care professions, as appropriate.

3 Sample size calculation

Cohort 1: A sample size of 200 patients will be able to detect an effect size of 0.30 with 89% power after adjusting for multiplicity of testing changes in 15 primary variables, at an overall significance level of 0.05.

In addition, for both cohorts the primary interest is to estimate mean change from Baseline at various time points (Months 3, 6, and 12) of the primary and secondary variables. A sample size of 200 patients in each cohort will provide us the precision of estimates within 0.14 of the corresponding standard deviation of the variables of interest.

4 Change to protocol specified analyses

Not applicable.

5 Appendix

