9.5.2 Safety variables

The assessment of safety will be based mainly on the frequency of adverse events.

Adverse events will be summarized by presenting the number and percentage of patients having any adverse event, having an adverse event in each system organ class and having each

individual adverse event by cohort and overall. Any other information collected (e.g., severity or relationship to fingolimod) will be summarized, as appropriate.

Serious adverse events and adverse events leading to discontinuation of study will be summarized by system organ class and preferred term for each cohort and overall.

Safety Set will be used for the following analyses.

In addition to variables presented in [Section 9.4.1](#), the following secondary variables will be analyzed:

1. Change from Baseline to Months 3, and 12 in CD4+ naïve T cells (CCR7+CD45RA+);
2. Change from Baseline to Months 3, and 12 in CD4+ central memory T cells (CCR7+CD45RA-CD45RO+);
3. Change from Baseline to Months 3, and 12 in CD4+ effector memory T cells (CCR7-CD45RA-CD45RO+);
4. Change from Baseline to Months 3, and 12 in CD4+ Th1 cells (CXCR3+);
5. Change from Baseline to Months 3, and 12 in CD4+ Th2 cells (CCR4+);
6. Change from Baseline to Months 3, and 12 in CD4+ Th17 cells (CCR6+);
7. Change from Baseline to Months 3, and 12 in CD8+ naïve T cells (CCR7+CD45RA+);
8. Change from Baseline to Months 3, and 12 in CD8+ central memory T cells (CCR7+CD45RA-CD45RO+);
9. Change from Baseline to Months 3, and 12 in CD8+ effector memory T cells (CCR7-CD45RA-CD45RO+);
10. Change from Baseline to Months 3, and 12 in naïve B cells (CD19+CD27-);
11. Change from Baseline to Months 3, and 12 in memory B cells (CD19+CD27+);
12. Change from Baseline to Months 3, and 12 in regulatory B cells (CD19+CD24+CD38+);
13. Change from Baseline to Months 3, and 12 in monocytes (CD14+);
14. Change from Baseline to Months 3, and 12 in neutrophils (CD16+);
15. Change from Baseline to Months 3, and 12 in NK cells (CD56+);
16. Change from Baseline to Months 3, 6, and 12 in the anti-JCV antibody index;
17. Change from Baseline to Months 3, 6, and 12 in Hematology measurements;
18. Anti-JCV antibody status (+ or -) at Months 3, 6, and 12.

[figure not shown]
For Variable 18, frequency count and percentage together with the 95% confidence interval for the proportion of JCV antibody positive patients will be presented.

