2.2 Analysis sets

Enrolled Set: All patients enrolled in one of the two cohorts will be included in the Enrolled Set.

Safety Set: The Safety Set will include all patients who enrolled in one of the two cohorts and received at least one dose of fingolimod during the study. Patients will be analyzed according to the cohort enrolled.

Full Analysis Set: For this study, the Full Analysis Set is the same as the safety set defined above.

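### Adverse events at the Cohort 2 safety interim and the Month 6 analysis are planned only as crude percentages, which estimate risk over no defined period because follow-up is unequal at both cuts

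*SAP*

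**What the plan says.** SAP 2.9 plans two looks before the final Month 12 analysis.

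- **First interim.** Its purpose is an early safety assessment of Cohort 2, and its trigger is "This will be conducted when 50% of patients in Cohort 2 have completed the Month 6 follow up". It covers one cohort and is descriptive: "The first interim analysis is a summarization of data from Cohort 2 only and no confirmatory hypothesis will be tested".
- **Month 6 (primary) analysis.** "This analysis will be conducted when all patients in Cohorts 1 and 2 complete Month 6 (primary time point of interest) of study". It is not truncated at Month 6: "All data collected on patients from both Cohorts 1 and 2 will be included in this analysis".

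Results of both may be published externally (SAP 2.9).

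The AE measure is the same at every look. SAP 2.8.4: "All TEAEs will be summarized by presenting the number and percentage of patients having at least one TEAE". For serious events, SAP 2.8.4.1 uses the word rates but defines them as percentages: "Summaries of incidence rates (frequencies and percentages) of serious AEs by SOC and PT will be prepared". Protocol 9.5.2 displays each "individual adverse event by cohort and overall". The denominator is the Safety Set, whose members need only have "received at least one dose of fingolimod during the study" (SAP 2.2), with no minimum follow-up.

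Duration of exposure is described separately in SAP 2.6 and is not linked to the AE counts. No person-time rate, time-to-first-event estimate or fixed-window AE table is planned. SAP 2.1.1 mentions a cut-off date, but the visible text does not define one for either look.

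**The concern.** The proportion of patients with an event estimates a risk only when everyone has been observed for the same, stated time. At these two cuts follow-up is staggered by date of entry. A patient who entered Cohort 2 the week before the first interim counts fully in the denominator and contributes almost no time in which an event could occur. The percentage is therefore a mixture of risks over different periods, and the mixture depends on accrual.

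What is at stake is interpretation. The first interim exists to inform about safety, and both sets of results may be published before the Month 12 tables exist. A reader could take the figure for a 6-month or a 12-month risk, and the plan does not say which, if either, it estimates.

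**Working it through.** **The plan's own figures.** No AE rate or follow-up distribution is stated, so there is none to reproduce on this point. The sample-size figures do reproduce: a two-sided one-sample t-test at 0.05/15 with N = 200 and effect size 0.30 gives 89.6% power (stated 89%), and 1.96/√200 = 0.139 (stated 0.14). Nothing below depends on them.

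**Inputs from the documents.** 200 patients per cohort; maximum follow-up 12 months; first interim when half of Cohort 2 has reached Month 6; Month 6 analysis when all patients have; simultaneous recruitment ending 30 June 2018 (Protocol 3.1, 6.3).

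**Assumptions.** Uniform accrual over R months, with R from 6 to 24; no dropout; 12-month risk 20%; constant hazard h = −ln(0.8)/12 = 0.0186 per month; all treated Cohort 2 patients counted at the first interim; the 50% taken on the planned 200. The 6-month risk is 1 − exp(−6h) = 10.6%.

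**Formula.** For follow-up uniform on a to b months, the expected crude percentage is C(a,b) = 1 − [exp(−ha) − exp(−hb)] / [h(b − a)]. Patients already at 12 months contribute 20%.

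**First interim**, at R/2 + 6 months:

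| R (months) | Follow-up | Calculation | Crude % |
|---|---|---|---|
| 6 | 3–9, mean 6.0 | C(3,9) | 10.5 |
| 12 | 0–12, mean 6.0 | C(0,12) | 10.4 |
| 18 | 0–12, mean 7.2 | 0.20 × 20 + 0.80 × 10.4 | 12.3 |
| 24 | 0–12, mean 8.0 | ⅓ × 20 + ⅔ × 10.4 | 13.6 |

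The share with under 6 months is 50%, 50%, 40% and 33% respectively.

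**Month 6 analysis**, at R + 6 months, with C(6,12) = 15.4%:

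| R (months) | Share at 12 months | Calculation | Crude % |
|---|---|---|---|
| 6 | 0 | C(6,12) | 15.4 |
| 12 | 0.50 | 0.50 × 20 + 0.50 × 15.4 | 17.7 |
| 24 | 0.75 | 0.75 × 20 + 0.25 × 15.4 | 18.8 |

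So the same hazard reads about 10% to 14% at one cut and about 15% to 19% at the next.

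**Hazard shape.** With strongly early-loaded events (Weibull shape 0.3, same 20% at 12 months), the first interim reads 15.7% to 17.1%. The 6-month risk is then 1 − exp(−0.223 × 0.5^0.3) = 16.6%, so the 10.6% benchmark belongs to the constant-hazard case only.

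**Recruitment pace, Month 6 analysis only.** With equal pace the difference is zero. If Cohort 1 accrues over R and Cohort 2 over R/2, the same hazard gives 17.7% against 20.0% (R = 12, 2.3 points) or 18.8% against 20.0% (R = 24, 1.2 points).

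**Check of the remedy.** The true rate is −ln(0.8) × 100 = 22.3 per 100 patient-years in both cohorts. Simulating the R = 12 unequal-pace case gave crude 17.7% against 19.9%, and exposure-adjusted rates of 22.4 against 22.2. The adjustment removes the artefact when the hazard is constant.

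**The case against.** **The percentages are not biased in one direction.** A reader might infer that they understate risk. That holds only against the 12-month risk, and no document presents the interim figure as one. Against the 6-month risk, the first-interim figure is nearly equal for R of 6 or 12 (10.5% or 10.4% against 10.6%) and higher for longer accrual. The Month 6 figure exceeds the 6-month risk throughout. This part of the objection stands: the defect is an undefined period.

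**A cohort artefact is not established.** A reader might infer that the cohorts will look different through recruitment pace alone. The first interim has no second cohort. At Month 6 a difference needs unequal pace, whereas Protocol 3.1 plans simultaneous recruitment and gives no pace for either cohort. Cohort 2 is also a referent, not a comparator (SAP 1.1). This stands too. The extreme of one cohort wholly at 6 months and the other wholly at 12 (10.6% against 20.0%) is only a bound.

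**The plan has mitigations.** Exposure is summarised, all data are listed, the looks are descriptive, and a Month 12 analysis follows with nearly equal planned follow-up. These help only in part. SAP 2.1.1 and 2.6 count exposure from the first non-zero dose, and Protocol 6.4.5 collects Cohort 2's first treatment date at screening, so exposure may include two or more pre-study years. A later table also does not correct a figure already published.

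**Part of the text is hidden.** A sentence in SAP 2.1 on how the interim and final analyses are performed is blacked out, so a cut-off rule may exist there. That limits what can be said about cut-offs, but the choice of AE measure in SAP 2.8.4 is fully visible.

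**Conclusion.** The point holds, and it is one of interpretation. At the Cohort 2 safety interim and the Month 6 analysis, AEs and serious AEs are reported only as crude percentages under staggered follow-up, so they estimate risk over no defined period. The problem is greater at the first interim, where follow-up can run from 0 to 12 months, than at the Month 6 analysis, where patients still in the study have at least about 6.

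Accrual duration, hazard shape, AE risk and zero dropout are all assumptions, and the size of the effect moves with them; early-loaded events narrow the gap to the 12-month risk. A general understatement of risk, or an actual cohort difference from pace, is not supported. The change is worth making because the first interim's purpose is safety, its results may be published, and the remedy is cheap.

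**What to change.** In SAP 2.8.4 and 2.9:

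1. State the data cut-off for each interim (unless the blacked-out text already does) and that the first interim uses all Cohort 2 Safety Set patients. Restricting it to those who completed Month 6 would drop early leavers, including any who left because of an AE.
2. Beside the crude percentages add, for any TEAE, serious AEs and each SOC/PT, the exposure-adjusted incidence: patients with a first on-study event per 100 patient-years at risk. Start time at risk at the study Baseline visit (on-study Day 1), not at the first-ever fingolimod dose.
3. Show person-years and median follow-up by cohort.
4. At the Month 6 analysis, a fixed 0–6 month AE table is an acceptable alternative to item 2.

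Crude percentages can stay as the main display at Month 12.

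**Cost.** SAP wording and additional table columns, with no new data collection. An on-study start date must be derived for Cohort 2, and time at risk computed separately for each event term. The rates assume a roughly constant hazard, which is least safe for patients starting treatment; showing person-years and median follow-up beside them lets the reader judge this.

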5.1 Imputation rules

In general, other than for partial dates, missing data will not be imputed and will be treated as missing.

Partial date will be imputed as below:

- If year is missing (or completely missing), do not impute;
- 15th of the month will be used to impute the initial diagnosis date if only the day is missing;
- July of the year will be used to impute as the initial diagnosis date if both the day and the month are missing;

5.1.1 Concomitant Medications Start/End Date

Partial missing start/end date to concomitant medications will be imputed as below:

Start date of concomitant medications

- If only the day of the month is missing, use the first day of the month to replace the missing part.
- If both the day and the month are missing, January 1st will be used to replace the missing part.
- If Day, Month and Year are all missing, use a date one day before the first date of fingolimod treatment.

End date of concomitant medications

- If only Day is missing, use the last day of the month.
- If Day and Month are both missing, use the last day of the year.
- If Day, Month and Year are all missing, assign ‘continuing’ status to stop date

5.1.2 Adverse Events Start/End Date

Missing or partial missing date to the onset date of AE will be imputed as below:

- If the AE onset date is completely missing, the AE start date will be imputed as the first date of fingolimod treatment;

- If the AE onset date is partial missing, then
 - If both the year and the month are available and the year and the month are the corresponding year and month of the first dosing date, then the AE start date will be imputed as the first dosing date;
 - If both the year and the month are available and the year and the month are not equal to the corresponding year and month of the first dosing date, then the AE start date will be imputed as the 1st date of the month;
 - If only the year is available and the available year is the corresponding year of the first dosing date, then the AE start date will be imputed as the first dosing date;
 - If only the year is available, and the available year is not equal to the corresponding year of the first date of fingolimod treatment, then the AE start date will be imputed as the January 1st of the year;

Adverse event end date will be imputed as below for the partial date only.

- If both the year and the month are available, AE end date will be imputed as the last day of the month;
- If only the year is available, AE end date will be imputed as the December 31st of the year.

If the imputed AE end date is after the death date, then the date of the death will be imputed as the AE end date.

For adverse events continuing at the cut-off date, the end date will not be imputed and instead will be reported as “ongoing”.

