7.1 Adverse events

An adverse event is any untoward medical occurrence (e.g., any unfavorable and unintended sign [including abnormal laboratory findings], symptom or disease) in a subject or clinical investigation subject *after providing written informed consent* for participation in the study until the end of study visit. Therefore, an AE may or may not be temporally or causally associated with the use of fingolimod.

In addition, all reports of intentional misuse and abuse of the product are also considered an adverse event irrespective if a clinical event has occurred.

The occurrence of adverse events must be sought by non-directive questioning of the patient at each visit during the study. Adverse events also may be detected when they are volunteered by the patient during or between visits or through physical examination findings, laboratory test findings, or other assessments.

Abnormal laboratory values or test results constitute adverse events only if they fulfill at least one of the following criteria:

- they induce clinical signs or symptoms,
- they are considered clinically significant,
- they require therapy.

Clinically significant abnormal laboratory values or test results must be identified through a review of values outside of normal ranges/clinically notable ranges, significant changes from baseline or the previous visit, or values which are considered to be non-typical in patient with underlying disease. Investigators have the responsibility for managing the safety of individual patient and identifying adverse events. Alert ranges for laboratory and other test abnormalities are included in [Appendix 2](#).

Adverse events must be recorded in the Adverse Events eCRF under the signs, symptoms or diagnosis associated with them, accompanied by the following information:

the severity grade

- mild: usually transient in nature and generally not interfering with normal activities
- moderate: sufficiently discomforting to interfere with normal activities
- severe: prevents normal activities

its relationship to the Fingolimod treatment

- Yes
- No

All adverse events must be treated appropriately. Treatment may include one or more of the following:

- no action taken (e.g., further observation only)
- Fingolimod treatment dosage increased/reduced
- Fingolimod treatment interrupted/withdrawn
- concomitant medication or non-drug therapy given
- non-drug therapy given

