2.7 Analysis of the primary objective

2.7.1 Primary endpoint

All analyses will be conducted by cohort for the Safety Set. There are 22 primary endpoints for this study, and Change from Baseline to Month 6 will be calculated as:

Change from baseline to Month 6 = Observed Value at Month 6 (Days 136 to 270) – Baseline Value

1. Change from Baseline to Month 6 in CD4+ naïve T cells (CCR7+CD45RA+)
2. Change from Baseline to Month 6 in CD4+ central memory T cells (CCR7+CD45RACD45RO+)
3. Change from Baseline to Month 6 in CD4+ effector memory T cells (CCR7-CD45RACD45RO+)
4. Change from Baseline to Month 6 in CD4+ Th1 cells (CXCR3+)
5. Change from Baseline to Month 6 in CD4+ Th2 cells (CCR4+)
6. Change from Baseline to Month 6 in CD4+ Th17 cells (CCR6+)
7. Change from Baseline to Month 6 in CD8+ naïve T cells (CCR7+CD45RA+)
8. Change from Baseline to Month 6 in CD8+ central memory T cells (CCR7+CD45RACD45RO+)
9. Change from Baseline to Month 6 in CD8+ effector memory T cells (CCR7-CD45RACD45RO+)
10. Change from Baseline to Month 6 in naïve B Lymphocytes (CD19+CD27-)
11. Change from Baseline to Month 6 in memory B Lymphocytes (CD19+CD27+)
12. Change from Baseline to Month 6 in regulatory B Lymphocytes (CD19+CD24+CD38+)
13. Change from Baseline to Month 6 in monocytes (CD14+)
14. Change from Baseline to Month 6 in neutrophils (CD16+)
15. Change from Baseline to Month 6 in NK cells (CD56+)
16. Change from Baseline to Month 6 in Total CD4+ Absolute Cell Counts
17. Change from Baseline to Month 6 in Total CD4+ Differential Cell Counts
18. Change from Baseline to Month 6 in Total CD8+ Absolute Cell Counts
19. Change from Baseline to Month 6 in Total CD8+ Differential Cell Counts
20. Change from Baseline to Month 6 in Total CD19+ Absolute Cell Counts
21. Change from Baseline to Month 6 in Total CD19+ Differential Cell Counts

Descriptive statistics (sample size, mean, standard deviation, standard error of mean, minimum, first quartile, median, third quartile, interquartile range, and maximum) will be provided. The 95% confidence interval for the mean will be calculated.

Analyses will be performed with respect to the actual value of primary variables by employing an analysis of covariance (ANCOVA) model with gender as a factor and duration of disease at Baseline (either time since first symptom or time since diagnosis) and corresponding baseline as covariates. The unadjusted as well as the adjusted least squares means will be provided together with a p-value.

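### SAP date imputation ignores known dates: an AE that ended in screening can become treatment-emergent, and an imputed diagnosis can fall after Day 1

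*SAP*

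**What the plan says.** **Adverse event onset (SAP 5.1.2).** Three onset patterns go to first dose:

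- Wholly missing: "If the AE onset date is completely missing, the AE start date will be imputed as the first date of fingolimod treatment".
- Known to the month, and that month and year are those of first dose: "then the AE start date will be imputed as the first dosing date".
- Known to the year only: "If only the year is available and the available year is the corresponding year of the first dosing date", with the same result.

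A known month or year that differs from first dose goes to the first of that month or to 1 January of that year. The one bound in the section acts on end dates: "If the imputed AE end date is after the death date, then the date of the death will be imputed as the AE end date".

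**Treatment emergence (SAP 2.8.4).** These are "AEs that started or worsened in severity on or after the first dose of fingolimod treatment", up to 14 days after the last treatment date. Events that ended before dosing are not excluded.

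**Collection.** Protocol 7.1 counts events from the point "after providing written informed consent". Protocol Table 6-1 marks AE/SAE at screening, and Protocol 3.1.1 allows up to four weeks of screening.

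**Diagnosis date (SAP 5.1).** A missing day becomes the 15th. If the month is missing too, "July of the year will be used to impute as the initial diagnosis date if both the day and the month are missing", with no day named. A missing year is not imputed. Nothing compares the result with Day 1.

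**Use of that date.** The primary ANCOVA adjusts for "duration of disease at Baseline (either time since first symptom or time since diagnosis", so the choice of duration is open. SAP 2.3.4 computes these times as diagnosis date minus Day 1 plus one day, and prints a diagnosis date in the first-symptom formula as well.

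**The concern.** Sending an uncertain onset to first dose is a reasonable cautious default when nothing else is known. A recorded end date before first dose is something known: it shows that the event was over before the drug was started. The SAP does not use it, so the rule can produce a record that contradicts itself.

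SAP 2.8.2 bases the safety assessment mainly on adverse event frequency. Cohort 1 is where treatment begins, so a screening event moved to Day 1 would be read as an event at initiation.

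The diagnosis rule has the same gap. A date after Day 1 means that the patient was treated before being diagnosed, and that value enters a covariate of the primary model.

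**Working it through.** No figure stated in the plan is in dispute. The check applies the rules as written to example dates.

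**1. Adverse event rule.** Take first dose on 20 March 2018 and a recorded AE end of 10 March 2018.

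| Recorded onset | Imputed onset | Treatment-emergent? | Onset after end? |
|---|---|---|---|
| wholly missing | 20 Mar 2018 | yes | yes, by 10 days |
| Mar 2018 | 20 Mar 2018 | yes | yes, by 10 days |
| 2018 | 20 Mar 2018 | yes | yes, by 10 days |
| Feb 2018 | 1 Feb 2018 | no | no |
| 2017 | 1 Jan 2017 | no | no |

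The fault occurs in exactly the three patterns that SAP 5.1.2 sends to first dose. Events with complete dates are unaffected.

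The documents do not say how often onsets are partial. They do allow a conditional figure under an assumption. Suppose screening onsets are spread evenly over the 28 days before Day 1 (mean 14.5 days before) and Day 1 is spread evenly over a year. The share moved to Day 1 is then about:

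- day missing: 1 − 14.5/30.4 = 52%
- year only: 1 − 14.5/365 = 96%
- wholly missing: 100%

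These are shares of screening events that already have a partial or missing onset. They are not shares of all events. The self-contradiction arises only in those that also ended before Day 1.

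**2. Diagnosis rule, year only.** Take diagnosis recorded as 2018 and Day 1 on 1 March 2018. Duration in the natural direction is (Day 1 − diagnosis + 1)/365.25. SAP 5.1 gives no day in July, so both ends are shown.

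- 1 July is 122 days after Day 1: (−122 + 1)/365.25 = −0.33 years.
- 31 July is 152 days after Day 1: (−152 + 1)/365.25 = −0.41 years.

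The formula printed in SAP 2.3.4 reverses the subtraction, so the SAP's own output would be (122 + 1)/365.25 = +0.34 to (152 + 1)/365.25 = +0.42. Under that formula every patient diagnosed more than one day before Day 1 is negative, so this patient is still on the wrong side of zero. The reversal alone does not alter the ANCOVA fit, because printed value = 2/365.25 − correct value, which is a linear recoding. It does make the baseline summary wrong.

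If diagnosis and Day 1 share a calendar year, the imputed date falls after Day 1 for 181 of 365 possible Day 1 dates (50%, using 1 July) to 211 of 365 (58%, using 31 July).

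**3. Diagnosis rule, day missing.** With diagnosis March 2018 and Day 1 on 5 March, the imputed date is 15 March: (−10 + 1)/365.25 = −0.02 years. If the two share a month, this happens for about 14 of 30.4 days (46%).

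**4. Size of the covariate error.** The true date in step 2 is no earlier than 1 January, so the error is at most 181 days (0.50 years, 1 July) to 211 days (0.58 years, 31 July).

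**5. Which cohort.** Cohort 2 patients take fingolimod throughout screening, so the before-and-after-first-dose error chiefly matters in Cohort 1. If Day 1 is the study baseline, a Cohort 2 diagnosis in the same year cannot arise, given at least two years on drug and diagnosis before treatment. SAP 2.1.1, however, defines Day 1 as the first non-zero dose, which in Cohort 2 could be read as a date years before the study.

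**The case against.** The best case for leaving the rules alone is that the cases are few and the errors cautious. The adverse event fault needs a partial or missing onset together with an end before dosing. Validation checks and queries (Protocol 8.2 and 8.3) should complete many such dates. Protocol 5.5.7 and 6.6 say that safety information is not solicited and speak of suspected drug reactions, which would limit pre-dose records. Moving doubtful onsets to first dose over-counts rather than under-counts, and with no comparator no between-arm contrast can be biased.

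Much of this stands as an argument about size. It does not rescue the rule. Protocol 7.1 and Table 6-1 call for collection from consent. The source-only provision for non-serious screening events (Protocol 6.1) sits in the section on screen failures, so it does not remove events in enrolled patients. Imputation exists for the dates that queries fail to complete, and caution is no reason to override a recorded end date.

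A reader might go further in two ways that the documents do not support.

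- *That the date rules are unbounded.* They are not: imputed AE end dates are capped at death, and a missing diagnosis year is left missing.
- *That patients will drop out of the primary analysis and cost power or precision.* SAP 5.1 has no rule for partial first-symptom dates, but this matters only if first-symptom duration is chosen, and SAP 2.7.1 leaves that open. The first-symptom formula in SAP 2.3.4 itself uses a diagnosis date. The documents give no share of partial symptom dates. The planned descriptive statistics and confidence interval for mean change need no covariate. SAP 2.7.2 states that there is no confirmatory hypothesis. No loss of power or precision can be derived, and the 89% power and 0.14 SD in SAP section 3 are not in question.

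**Conclusion.** The point holds as a narrow data-integrity fault. As written, SAP 5.1.2 and 2.8.4 together report an event that ended in screening as treatment-emergent, with onset after its end, whenever onset is wholly missing or known only to the month or year of first dose. SAP 5.1 can also place diagnosis after Day 1 when the two share a year or a month.

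Neither frequency can be derived from the documents. The conditional shares above rest on assumed even spreads of onset and Day 1. The adverse event part is the clearer one, because it changes a reported count. The diagnosis part is an error of about half a year at most in one adjustment covariate, so its effect on the adjusted means is probably small, although the documents do not allow it to be calculated. Both mainly concern Cohort 1. This is a minor point, worth correcting because the correction is simple.

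**What to change.** - **SAP 5.1.2.** Impute onset to first dose only if the AE end date is missing, ongoing or, after any end-date imputation, on or after first dose. Otherwise set onset to the later of consent and the first of the end month, which is never after the end date for an event arising after consent, and do not count the event as treatment-emergent. An event with only the first-dose month recorded for both onset and end stays treatment-emergent, because its end is imputed to month end and nothing contradicts the cautious default.
- **SAP 5.1.** Name the day in July and cap any imputed diagnosis date at Day 1. State which Day 1 applies to Cohort 2: study baseline or first-ever dose.
- **SAP 2.3.4.** Compute duration as Day 1 minus diagnosis date, and correct the date used in the first-symptom formula.
- **SAP 2.7.1 and 5.2.1.** Name time since diagnosis, for which partial-date rules exist, as the single ANCOVA duration covariate.

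The cost is a few SAP sentences and minor programming, with no new data and no change to sample size.
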